#### 8.4.4 Appropriateness of safety measurements

The safety assessments selected are standard for this indication/patient population. If there are any signs of IOI, additional assessments will be performed as described in Section 8.4.3.

## 8.5 Additional assessments

Not applicable

## 9 Study discontinuation and completion

### 9.1 Discontinuation

#### 9.1.1 Discontinuation of study treatment

Discontinuation of study treatment for a patient occurs when study treatment is stopped earlier than the protocol planned duration, and can be initiated by either the patient or the investigator.

The investigator must discontinue study treatment for a given patient if he/she believes that continuation would negatively impact the patient's well-being.

The investigator and/or referring physician will recommend the appropriate follow-up medical care, if needed, for all patients who are prematurely withdrawn from the study.

Study treatment must be discontinued under the following circumstances:

- Patient requires treatment on a q4w interval after the initiation phase, i.e., after the three monthly injections at Baseline, Week 4, and Week 8, followed by the first interval extension
- Patient develops intraocular inflammation, including retinal vasculitis and/or retinal vascular occlusion
- Patient/guardian decision
- Pregnancy
- Use of prohibited treatment
- Any situation in which study participation might result in a safety risk to the patient

If premature discontinuation of study treatment occurs, the following should be done as appropriate:

- The investigator should make a reasonable effort to understand and document the primary reason for the patient's premature discontinuation of study treatment using the appropriate eCRF page.
- Patients who prematurely discontinue study treatment for any reason should return 4 weeks after last study treatment to perform the assessments for early treatment discontinuation (ETD). Please refer to [Table 8-1](#), except for patients who withdraw their consent from the study and do not wish to do so (refer to [Section 9.1.2](#)).
- After these assessments are performed, patient can be switched to standard of care (SOC) anti-VEGF IVT as per investigators discretion. IVT injection is contraindicated in patients with active intraocular or periocular infections and in patients with active intraocular inflammation; therefore, the investigators must verify that these conditions are not present in the study eye prior to every injection.
- After premature study treatment discontinuation, at a minimum till week 48, in abbreviated visits, the following data should be collected at clinic visits or via telephone/email contact:
  - New/concomitant treatments

- Adverse events/Serious Adverse Events
- BCVA

Additional safety assessments and imaging can be performed if required, as per investigator's discretion.

Dosing of SOC and follow-up visits as per investigators discretion. Patients are not required to attend the mandatory visits at Week 16 and Week 48.

- Patients who decide not to participate in the study further should NOT be considered withdrawn from the study, UNLESS they withdraw their consent (see [Section 9.1.2](#)). **Where possible, patients should return for the EOS visit assessments to be performed as scheduled in [Table 8-1](#).** EOS visit assessments on [Table 8-1](#) do not need to be repeated at week 48 for patients on standard of care as they would have been performed as ETD assessment prior to standard of care switch.
- If a patient fails to return for study visits without stating an intention to discontinue or withdraw, the investigator must show "due diligence" by documenting in the source documents steps taken to contact the patient, e.g. dates of telephone calls, registered letters, etc. A patient should not be considered as lost to follow-up until due diligence has been completed (see [Section 9.1.3](#)). If the patient cannot or is unwilling to attend any visit(s), the site staff should maintain regular telephone contact with the patient, or with a person pre-designated by the patient. This telephone contact should preferably be done according to the study visit schedule.

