 Intraocular pressure (IOP) will be assessed in the study eye, pre-dose and post-dose at every injection. The same method of tonometry has to be used through the whole study. Close monitoring of IOP should be performed by the investigator for any non-transient elevation in IOP ( $\geq 25$  mmHg). Intravitreal injection is not recommended unless normalization of the IOP has been achieved. Post-dose IOP should be assessed within 60 minutes after injection and if  $\geq 25$  mmHg, assessment should be repeated until back to normal. Monitoring of the optic nerve head perfusion after injection may be appropriate, at the discretion of the investigator. Results of these procedures will be recorded as appropriate in the source documents and if the findings constitute an AE, it should be recorded in the eCRF.

 Additional ophthalmic examinations and images will be performed in case of any signs of intraocular inflammation (IOI), retinal vasculitis, and/or retinal vascular occlusion.

 A telephone follow-up on safety should be performed one week after the first injection (a window for the phone call is +7 days). From the second injection onwards, similar phone calls should be made at investigator's discretion per local practice.

 The week 48 EOS assessments only apply to patients who completed the study per protocol. The assessments are not required for patients who have undergone ETD assessments and continued in the study without study treatment.

 ETD: Early treatment discontinuation applies to patients who discontinue early from study treatment and continue in the study. The assessments should be performed 4 weeks after the last injection of study drug. This can occur at any time point.

 For patients who continue in the study after ETD and up to Week 48 (end of study) while patient is on standard of care. Additional safety assessments and imaging can also be performed if required, as per investigators discretion. In addition, after ETD, subjects are not required to attend the mandatory visits at Week 12 and Week 48. The last visit should be at week 48. This can occur at any time point.

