### **8.3.3 Visual acuity**

Visual acuity will be assessed in the study eye at the visits indicated in the visit assessment schedule as described in [Table 8-1](#) using best correction determined from protocol refraction (via BCVA). BCVA of the fellow eye will be assessed at Screening/Baseline and at Week 48/EOS Visit. BCVA measurements will be taken in a sitting position using ETDRS-like visual acuity testing charts at an initial testing distance of 4 meters.

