2.6.1.4 Best corrected visual acuity (BCVA)

The summary statistics (n, mean, std, median, min and max) of BCVA for nAMD patients will be presented along with change and percentage change from Baseline in BCVA by visit. Along with below BCVA category.

- 1. BCVA (≤ 55 , 56 70 and ≥ 71).
- 2. Increase of ≥ 5 , ≥ 10 and ≥ 15 letters in BCVA from Baseline up to Week 48.
- 3. Loss of ≥ 5 , ≥ 10 , ≥ 15 and ≥ 30 letters in BCVA from Baseline up to Week 48.
- 4. BCVA \geq 84.

The above analysis will be done only on the study eye. The analysis will be performed on FAS.

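### After a treatment stop the protocol allows BCVA to be collected by telephone or email and contradicts itself on Week 48 attendance, so late ETDRS vision may be missing or invalid where the safety analysis needs it

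*Protocol*

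**What the plan says.** Protocol 9.1.1 sets how long follow-up lasts once a patient has stopped early: "After premature study treatment discontinuation, at a minimum till week 48, in abbreviated visits". On the mode of collection, it allows remote contact as an alternative to attendance: "the following data should be collected at clinic visits or via telephone/email contact". The list that follows has three items: new or concomitant treatments, adverse events, and BCVA. Protocol 8.3.3 fixes how BCVA is obtained, using the correction from the protocol refraction: "BCVA measurements will be taken in a sitting position using ETDRS-like visual acuity testing charts at an initial testing distance of 4 meters". Table 8-1 labels the row as an ETDRS score and marks it in every column, including the last one (M), which covers patients who stay in the study after the ETD visit.

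On Week 48 the texts diverge.

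- Section 9.1.1 waives it: "Patients are not required to attend the mandatory visits at Week 16 and Week 48". It adds that the end-of-study (EOS) assessments "do not need to be repeated at week 48 for patients on standard of care as they would have been performed as ETD assessment".
- Table 8-1, footnote 10, does not require the Week 48 EOS assessments after ETD. Footnote 12 says that "after ETD, subjects are not required to attend the mandatory visits at Week 12 and Week 48".
- The same footnote then says: "The last visit should be at week 48".
- The closing paragraph of the Section 8 introduction asks everyone who stops early, for any reason, to return for the EOS assessments unless consent is withdrawn. Section 9.1.1 asks the same, where possible, of patients who decide not to take part further.

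The two waivers also name different visits: Weeks 12 and 48 in footnote 12, Weeks 16 and 48 in Section 9.1.1.

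**The concern.** Treatments and adverse events can be taken by telephone. An ETDRS letter score cannot. A value reported by telephone or email would be on another scale or recalled from another examination, and the SAP gives no rule for handling it.

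The patients affected include those whose late vision matters most for safety. Protocol 6.1.4, 8.4.3, 9.1.1 and 10 require study treatment to stop once IOI, including retinal vasculitis and/or retinal vascular occlusion, is confirmed. Sections 1.1 and 4.5 say these events may cause severe vision loss. SAP 2.9.1.1 plans summary statistics and plots of change from baseline in BCVA after the end date of each type of adverse event of special interest (AESI). If BCVA after the stop is absent or not an ETDRS score, that summary cannot show whether vision recovered.

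**Working it through.** **1. Can a site comply and hold no late score?** The ETD visit, 4 weeks after the last injection, includes an ETDRS score. After it, Section 9.1.1 accepts remote contact and waives Week 48, and footnotes 10 and 12 agree on the waiver. A site following those three texts is compliant with no measured BCVA after ETD. A site following Section 8, column M and the last-visit sentence of footnote 12 would measure one. The protocol does not say which prevails, so a late score is possible but not guaranteed.

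**2. How long is the unprotected period?** Gap to Week 48 = 48 − (week of last injection + 4).

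| Last injection | ETD week | Gap (weeks) |
|---|---|---|
| Day 1 | 4 | 44 |
| Week 4 | 8 | 40 |
| Week 8 | 12 | 36 |
| Week 16 | 20 | 28 |
| Week 20 | 24 | 24 |
| Week 24 | 28 | 20 |
| Week 32 | 36 | 12 |

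A patient who has had the last planned injection, at Week 40 or Week 44, has no treatment left to stop and goes to the ordinary Week 48 EOS visit with an ETDRS score.

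**3. How many patients?** The plan gives no figure for missing late BCVA, so there is none to reproduce. The denominator does reproduce: (1.96 × 35 / 5)² = 188.2, rounded up to 189, and 189 / 0.90 = 210. Protocol 4.5 cites IOI-related events in 3.2% of men and 5.3% of women in the pivotal trials. Assuming each rate in turn applies to all 210 patients:

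- 210 × 0.032 = 6.7, about 7 (95% binomial range 2 to 12)
- 210 × 0.053 = 11.1, about 11 (95% binomial range 5 to 18)

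In a group of 7 to 11, one absent or invalid score is 1/11 = 9% to 1/7 = 14% of the group, and more within a single AESI type.

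**4. Which analyses use these scores?**

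- *Efficacy.* Protocol 12.4.1 targets the effect while on study treatment. Protocol 12.4.3 censors efficacy data when study treatment stops, and 12.5.1 analyses continuous functional outcomes by the primary method. SAP 2.1.1 is less clear, saying that efficacy data are used at the time of the stop. SAP 2.6.1.4 lists gains and losses of "letters in BCVA from Baseline up to Week 48" without mentioning stopped patients. If 12.4.3 governs, scores after the stop do not enter these summaries, however well they are measured.
- *Safety.* SAP 2.9.1.1 needs BCVA after the AESI end date. For an event that resolves after the ETD visit, only scores taken after ETD can supply it.

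**The case against.** The best defence is that the protocol already captures most of what is needed. Clinic visits stand beside telephone and email as an equal option, and column M specifies the ETDRS scale. Section 8 and footnote 12 both point to a return at the end of the study. Patients with symptoms are to be seen at once, and an unscheduled visit whose finding leads to an adverse event requires all Interim Visit procedures, which include ETDRS BCVA. The ETD visit adds another score, and adverse events are followed until resolved or judged permanent. Lighter follow-up after a switch to standard of care was added deliberately in Amendment 3.

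Much of this stands. A reader might infer that late vision is missing in every IOI case. The documents do not support that: clinic measurement remains open, scores at the event and at ETD are planned, and IOI arising after the last planned injection leaves the Week 48 EOS visit in place.

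It does not answer the point fully. Scores at onset and at ETD may precede the end of the event, whereas the SAP asks for BCVA after it. Following an adverse event to resolution does not itself require a letter score. Lighter follow-up is a fair choice, but listing BCVA among items that may be collected by email does not fit the protocol's own definition of BCVA.

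The count of 7 to 11 is also open to challenge. The rates are sex-specific, come from trials that ran to 96 weeks, and are cited without a time frame. This trial lasts 48 weeks and excludes IOI within the previous 12 months.

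**Conclusion.** The point holds as a gap and an internal contradiction in data collection after a stop. Late ETDRS BCVA may be missing or invalid in patients who stop before their last planned injection, including those with IOI, vasculitis or occlusion. This weakens the SAP 2.9.1.1 summary of BCVA after AESI and the safety reading of lasting vision loss. The unprotected period is 36 to 44 weeks after a stop in the loading phase, shrinking to 12 weeks after a last injection at Week 32. The 7 to 11 IOI cases are an assumption that the cited rates carry over to all 210 patients, and those arising after the last planned injection would not be affected.

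A reader might also infer that mean BCVA change at Week 48 is overstated and large letter losses under-counted. That does not follow if censoring under Protocol 12.4.3 governs: a perfect Week 48 score in a stopped patient would still be left out, so any difference comes from the on-treatment estimand and not from telephone contact. The documents give neither a rate of early stops nor a vision deficit in stopped patients from which to size such a bias. The primary endpoint is an OCT-A measure and is not touched by how BCVA is collected.

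**What to change.** 1. In Protocol 9.1.1, limit telephone and email contact to treatments and adverse events. State that BCVA after a stop is recorded only when measured in clinic by the method in 8.3.3.
2. Reconcile Section 8, Section 9.1.1 and footnotes 10 and 12 of Table 8-1, so that patients still in the study have one ETDRS BCVA at the Week 48 last visit that footnote 12 already names. Settle the Week 12 versus Week 16 mismatch in the waivers at the same time.
3. In SAP 2.9.1.1, report the number of AESI patients, and of stopped patients overall, without a post-event ETDRS score (for patients stopped without an AESI, a score after the stop).

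The cost is a short amendment touching several linked passages and one added line in the SAP tables. Some stopped patients would attend one clinic visit at Week 48 instead of taking a call. Standard-of-care dosing and all other follow-up stay at the investigator's discretion, and the rules for stopping treatment are unchanged.

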#### 9.1.1.1 Replacement policy

Patients who started treatment but prematurely discontinued treatment and/or study will not be replaced.

#### 9.1.2 Withdrawal of informed consent

Patients may voluntarily withdraw consent to participate in the study for any reason at any time. Withdrawal of consent occurs only when a patient:

- Does not want to participate in the study anymore, and
- Does not allow further collection of personal data.

In this situation, the investigator should make a reasonable effort (e.g. telephone, e-mail, letter) to understand the primary reason for the patient's decision to withdraw his/her consent and record this information.

Study treatment must be discontinued and no further assessments conducted, and the data that would have been collected at subsequent visits will be considered missing.

Further attempts to contact the patient are not allowed unless safety findings require communicating or follow-up.

All efforts should be made to complete the assessments prior to study withdrawal. A final evaluation at the time of the patient's study withdrawal should be made as detailed in the assessment table ([Table 8-1](#)).

Novartis will continue to keep and use collected study information. according to applicable law.

### **9.1.3 Lost to follow-up**

For patients whose status is unclear because they fail to appear for study visits without stating an intention to discontinue or withdraw, the investigator must show “due diligence” by documenting in the source documents steps taken to contact the patient, e.g. dates of telephone calls, registered letters, etc.

A patient should not be considered as lost to follow-up until due diligence has been completed.

### **9.1.4 Early study termination by the sponsor**

The study can be terminated by Novartis at any time. Reasons for early termination may include:

- Unexpected, significant, or unacceptable safety risk to patients enrolled in the study
- Discontinuation of study drug development
- Practical reasons, including slow enrollment
- Regulatory or medical reasons

In taking the decision to terminate, Novartis will always consider patient welfare and safety. Should early termination be necessary, patients must be seen as soon as possible and treated as a prematurely withdrawn patient. The investigator may be informed of additional procedures to be followed in order to ensure that adequate consideration is given to the protection of the patient’s interests. The investigator or sponsor depending on local regulation will be responsible for informing IRBs/IECs of the early termination of the trial.

## **9.2 Study completion and post-study treatment**

Study completion is defined as when the last patient finishes their EOS/Early Withdrawal Visit, and any repeat assessments associated with this visit have been documented and followed-up appropriately by the investigator, or in the event of an early study termination decision, the date of that decision.

After study completion, the patient may receive standard of care or other treatments, at the discretion of the investigator and/or referring physician, if needed.

## **10 Safety monitoring and reporting**

Patients should be closely monitored for adverse events.

For adverse events of special interest, intraocular inflammation, including retinal vasculitis and/or retinal vascular occlusion please ensure compliance with the following:

- Instruct the patient to contact the site for any changes in vision or any symptoms of Intraocular inflammation, including retinal vasculitis and/or retinal vascular occlusion, between scheduled visits (refer to the optional patient brochure). Every effort should be made to bring the subject for immediate examination.
- Close patient monitoring and thorough examination of the eye should be done to detect potential signs of inflammation ([Section 8.4.4](#)).
- When IOI, retinal vasculitis, and/or retinal vascular occlusion is present or suspected during a visit, investigators must perform thorough ophthalmic examination, and will conduct OCT,

fluorescein angiography and color fundus photography (preferably wide-field or with peripheral sweeps). The images are requested to be uploaded onto the CRC portal.

- If any signs of intraocular inflammation is present, an IVT injection must not be performed. Therefore investigators must verify that these conditions are not present in the study eye prior to every injection.
- If Intraocular inflammation, including retinal vasculitis and/or retinal vascular occlusion, is confirmed, patients should be discontinued from study treatment.
- Patients should be treated for these events promptly according to clinical practice.

For additional information related to safety assessments refer to [Section 6.7.2](#) and Section 8.4.4

## 10.1 Definition of adverse events and reporting requirements

### 10.1.1 Adverse events

An AE is any untoward medical occurrence (e.g. any unfavorable and unintended sign, symptom or disease) in a patient after providing written informed consent for participation in the study. Therefore, an AE may or may not be temporally or causally associated with the use of a medicinal (investigational) product.

The investigator has the responsibility for managing the safety of individual patient and identifying AEs.

Novartis qualified medical personnel will be readily available to advise on trial related medical questions or problems.

The occurrence of AEs must be sought by non-directive questioning of the patient at each visit during the study. AEs may also be detected when they are volunteered by the patient during or between visits or through physical examination findings, or other assessments.

AEs must be recorded in the Adverse Events eCRF under the signs, symptoms or diagnosis associated with them, accompanied by the following information (as far as possible) (if the event is serious refer to [Section 10.1.2](#)):

1. The severity grade (mild, moderate or severe as defined below)
  - mild: usually transient in nature and generally not interfering with normal activities
  - moderate: sufficiently discomforting to interfere with normal activities
  - severe: prevents normal activities
2. Its relationship to the study treatment and the ocular injection procedure. If the event is due to lack of efficacy or progression of underlying illness (i.e. progression of the study indication) the assessment of causality to study treatment will usually be 'Not suspected'. The rationale for this guidance is that the symptoms of a lack of efficacy or progression of underlying illness are not caused by the trial drug, they happen in spite of its administration and/or both lack of efficacy and progression of underlying disease can only be evaluated meaningfully by an analysis of treatment arms, not on a single patient.
3. Its duration (start and end dates) or if the event is ongoing, an outcome of not recovered/not resolved must be reported.

4. Whether it constitutes a SAE (see for definition of SAE) and which seriousness criteria have been met.
5. Action taken with the study treatment. All AEs must be treated appropriately. Treatment may include one or more of the following:
  - No action taken (e.g. Further observation only)
  - Investigational treatment interrupted/withdrawn
  - Concomitant medication or non-drug therapy given
  - Patient hospitalized/patient's hospitalization prolonged (see [Section 10.1.2](#) for definition of SAE)
6. Its outcome:
  - Not recovered/not resolved
  - Recovered/resolved
  - Recovered/resolved with sequelae
  - Fatal or unknown.
7. Its location (ocular event / non ocular event)

Conditions that were already present at the time of informed consent should be recorded in the medical history of the patient.

Adverse events (including lab abnormalities that constitute AEs) should be described using a diagnosis whenever possible, rather than individual underlying signs and symptoms.

Adverse event monitoring should be continued until 30 days (safety follow-up) after the last administration of study treatment (see “Post-treatment follow-up period” in [Section 3](#)).

Once an AE is detected, it must be followed until its resolution or until it is judged to be permanent (e.g. continuing at the end of the study), and assessment must be made at each visit (or more frequently, if necessary) of any changes in severity, the suspected relationship to the interventions required to treat it, and the outcome.

Information about adverse drug reactions for the investigational drug can be found in the IB.

Abnormal test results constitute AEs only if they fulfill at least one of the following criteria:

- they induce clinical signs or symptoms
- they are considered clinically significant
- they require therapy

Clinically significant abnormal test results must be identified through a review of values outside of normal ranges/clinically notable ranges, significant changes from Baseline or the previous visit, or values which are considered to be non-typical in patients with the underlying disease. Investigators have the responsibility for managing the safety of individual patients and identifying AEs.

